### 5.2 Baseline evaluation (conducted during ED/OrthoNow visit)

#### *How measures will be taken*

Baseline questionnaires will be conducted with subjects in all arms of the study over the phone during the enrollment call. The baseline questionnaires will occur immediately after the patient has verbally consented to participate in the study. A description of the questions (non-standardized internal items) and assessment measures are summarized below:

#### *Baseline Questions and Measures*

- Access to Primary Care question
  - Question which asks whether the patient has a primary care provider
- Analgesic and Opioid use questions
  - Analgesic and opioid use questions which assess opioid use in the ED and pain medications in the past week
- Nonpharmacological pain management use questions (e.g., deep breathing)
  - Questions to assess strategies patients have used besides medication to manage pain such as mindfulness, meditation, imagery, yoga, or visiting a chiropractor

- Brief Pain Inventory-Short Form^28
  - The BPI-SF is an 11-item measure that rates pain severity and interference over the past week on a 0-10 numeric scale with higher scores reflecting more pain severity and more pain interference.
- Recovery Questions
  - Two questions to measures how well patients expect to recover from their pain and how long they estimate recovery will take.
- Prior History of Chronic Pain
  - Two questions based on the 2010 National Health Interview survey to assess if patients have a history of chronic pain.
- ENRICHD Social Support Inventory (ESSI): item 4 and 5
  - The two items on the ESSI will assess perceived social support (how much a patient feels supported) and embedded social support (whether a patient has practical help with everyday tasks)
- Single Item Literacy Screen
  - The SILS uses one question to identify limited reading ability, which is a component of health literacy. It assesses how often one needs assistance reading materials provided by a doctor or pharmacy, on a scale from “never” to “always.”
- Tobacco Screening Measure
  - This tool was developed by the University of Maryland School of Medicine and entails 2 questions to screen whether the patient has smoked cigarettes or used tobacco products ever or in the past 30 days.
- Pain Catastrophizing Scale 4-item version
  - The PCS-4 measures rumination, magnification, and helplessness related to one’s pain experience by having patients rate the degree to which thoughts and feelings are associated with their pain on a 5-point scale, ranging from “not at all” to “all the time.”
- Pain Self-efficacy Questionnaire-4 item version
  - The PSEQ 4-item questionnaire measures how confident a patient feels they can accomplish activities despite their pain on a 6-point scale where 0 is “not at all confident” and 6 is “completely confident.”
- Patient Health Questionnaire-2
  - The PHQ-2 is a two-question assessment to measure the frequency of depressed mood on a 4-point scale.
- Generalized Anxiety Disorder-2 item^43
  - GAD-2 is a two-question assessment to measure the frequency of anxious mood, on a 4-point scale.
- Control Preferences Scale
  - The CPS measures shared decision-making regarding a patient’s treatment. It consists of 5 statements and patients pick which statement best describes the level of involvement they prefer in treatment decisions.
- PROMIS Global Health-Physical 2a

- The Patient-Reported Outcomes Measurement Information System (PROMIS) includes 2 questions related to the general physical health and ability to carry out physical activities on a 5 point-scale with higher scores reflecting better health and ability.
- PROMIS-Physical Function-4
  - The Patient-Reported Outcomes Measurement Information System (PROMIS) report of physical function includes four items that measure ability to do chores, ability to use stairs, walking, and running errands on a 5-point scale with higher scores reflecting less difficulty.

### 5.3 Follow-up evaluations

#### *How measures will be taken*

All follow-up questionnaires will be conducted with subjects in all arms of the study via a phone interview at 1 week and 1, 3, 6, and 12 months. A description of the questions (non-standardized internal items) and various assessment measures are summarized below:

#### *Questions and Measures conducted at 1 Week*

- Brief Pain Inventory-short form
  - *See Baseline assessment*
- Patient Global Impression of Change
  - The PGIC is a 1-item measure of how much patients feel their pain has improved since their ED visit on a 7-point scale ranging from “much better” to “much worse.”
- Preparedness and Confidence Questions
  - Assesses how prepared patients feel about their ability to manage their pain with 6 questions on a 5-point scale, from “not at all” to “very well.”
- Pain Self Efficacy Questionnaire 4-item
  - *See baseline assessment*
- Analgesic and Opioid use
  - *See baseline assessment*
- Nonpharmacological pain management use questions (e.g., deep breathing)
  - *See baseline assessment*
- Opioid-Related Symptom Distress Scale
  - The OR-SDS assesses subject-reported levels of frequency and severity concerning 10 side effects known to be associated with opioid medication. Added to this measure are 5 additional symptoms reflecting side effects for patients taking NSAIDs or acetaminophen. Symptom frequency and severity will be rated on a 4-point scale with higher scores reflecting increased frequency and greater severity.
- Pittsburgh Insomnia Rating Scale-2
  - The PIRS measures patient’s sleep quality in the past week via two questions on a 4-point scale.

- International Physical Activity Questionnaire-short form
  - The IPAQ is a 7-item measure to assess the intensity of physical activity and sitting time that the patient engages in as part of their daily life, measured in minutes/per week and time spent sitting.
- Healthcare Utilization Questions
  - Questions pertaining to the number of days in the hospital, number of visits to an ED or urgent care, and number of visits to non-ED or urgent care physicians since the patient's ED visit.

*Questions and Measures conducted at 1, 3, 6, 12 months*

- Brief Pain Inventory-short form
  - *See Baseline assessment*
- PROMIS Global Health 2a
  - *See 1-week assessment*
- PROMIS Physical Function-4
  - *See Baseline assessment*
- Pittsburgh Insomnia Rating Scale-2
  - *See 1-week assessment*
- Opioid and Analgesic Use Questions
  - *See baseline assessment*
- Nonpharmacological pain management use questions (e.g., deep breathing)
  - *See baseline assessment*
- Opioid-Related Symptom Distress Scale (side effects)
  - *See 1-week assessment*
- Health Utilization Questions
  - *See 1-week assessment*

## 5.4 Schedule of Events

Procedures	Enrollment / Baseline	Telecare (48-72 hrs after enrollment)	Week 1 Follow-up Call	1, 3, 6, and 12 Month Follow-up Call
Demographics	X			
Obtain verbal informed consent	X			
Randomization	X			
Administer educational video	i, ii			
Call with research nurse		i		
Data Collection Measures/Questions				
Assess access to primary care provider question	X			
Overview of analgesic use (opioid and non-opioid)	X		X	X
Use of other pain management strategies	X		X	X
Brief Pain Inventory-short form (pain severity only)	X			
Brief Pain Inventory-short form (pain severity and pain interference)			X	X
Pain recovery questions	X			
Prior history of chronic pain questions	X			
Pain Catastrophizing Scale-short form	X			
PROMIS Global Health-2a (prior to pain)	X			
PROMIS Physical Function (prior to pain)	X			
PROMIS Global Health-2a (including pain)	X		X	X
PROMIS Physical Function (including pain)	X		X	X
Patient Health Questionnaire (Prior to pain)	X			
Generalized Anxiety Disorder-2 (Prior to pain)	X			
Control Preference Scale	X			
Pain Self-efficacy questionnaire-4 item version	X		X	
Single Item Literacy Screen	X			
Tobacco Screening Measure	X			
Global Impressions of Change			X	X
Preparedness and Confidence questions			X	
Opioid specific questions*	X		X	X
Non-opioid analgesic questions	X		X	X
Analgesic side effects			X	X
Pittsburgh Insomnia Rating Scale			X	X
International Physical Activity Questionnaire			X	
Health Utilization questions*	X		X	X
COVID-19 activity questions				X**

i Subjects in Full intervention arm

ii Subjects in Video-only intervention arm

\*Data obtained through Electronic Health Record AND Questionnaires

\*\* month 3 only

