Efficacy Evaluations	
The Brief Pain Inventory-Short Form (BPI-SF), which uses 11 questions each assessed on a 0-10 scale measures patient's pain severity and pain interference over the past week. The BPI-SF will be used to assess intervention efficacy. An average score will be calculated from the patients' answers to 11 questions. The primary outcome is a composite

---

score at 1, 3, and 6 months using a longitudinal comparison. We will adjust for baseline pain severity.

---

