Reducing the Transition from Acute to Chronic Musculoskeletal Pain among Older Adults

(BETTER from Pain)

NCT number NCT04118595

Document Date 07/24/2022

**Reducing the Transition from Acute to Chronic
Musculoskeletal Pain among Older Adults**

(BETTER from Pain Study)

Statistical Analysis Plan

Version 1.1

This statistical analysis plan is an expanded version of the summary analysis plan included in the study protocol and supersedes the summary plan included in the study protocol. Any significant changes made to this analysis plan after study initiation will be documented herein.

1. Study Objectives

The objectives of this 3-arm randomized trial are as follows:

Objective 1: To evaluate the effects of two Shared Decision Making based interventions (full and video-only intervention) relative to Usual Care on musculoskeletal pain (MSP), as measured by the combined pain severity and interference scores from the Brief Pain Inventory Short Form (BPI-SF), through 6 months following the initial visit.

Sub-Objective 1a: To evaluate the intervention effects separately on the two components of the BPI-SF, pain severity and interference, evaluating both longitudinal change through 12 months and differences at discrete time points of 1, 3, 6, and 12 months.

Sub-Objective 1b: To evaluate the intervention effects over time on other key secondary outcomes, including opioid use, analgesic-related side effect frequency and severity, physical function, overall health, sleep quality, and healthcare utilization.

Objective 2: To assess the mechanisms by which the interventions (full and video-only) influence outcomes.

Objective 3: To estimate the incremental cost per case of persistent pain (defined as pain ≥ 4 on 0-10 scale present at one year) prevented by either the full or video-only intervention compared with usual care.

This document describes the analyses planned for Objectives 1 and 2, and other supporting quantitative analyses. The cost-effectiveness analysis to be applied for Objective 3 will be described elsewhere.

2. Study Design Overview

Four hundred patients presenting with acute MSP recruited from four sites (3 emergency departments (EDs) and one Urgent Care) will be randomized to one of three arms:

1. **Full Intervention** (video + telecare + primary care provided (PCP) communication)
2. **Video-only Intervention** (video but no telecare or PCP communication)
3. **Usual Care**

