Interference is measured using seven items assessing how much the pain interferes with seven daily activities or conditions. Each item is scored on a 0 to 10 scale, with 0 indicating “does not interfere” and 10 indicating “completely interferes”. A Pain Interference Score will be obtained as the mean of the non-missing items as long as at least 4 of the 7 items is non-missing (i.e., using item-mean imputation).

The primary outcome is the Combined Pain Severity and Interference Score, which will be obtained by averaging the Pain Severity and Pain Interference scores, assuming that neither is missing.

See https://www.mdanderson.org/documents/Departments-and-Divisions/Symptom-Research/BPI_UserGuide.pdf

b. Overall health measured by the PROMIS Global Health-Physical 2a

This scale consists of two items, each scored from 1 to 5 with higher scores indicating better global health. In the follow-up survey, these are the variables PHYHLTH and PHYACT. These items will both have to be reverse-scored prior to summing. Missing items will not be imputed. A total score is computed by summing these two items, and is then converted to a t-score for analysis using the table below.²

PROMIS Global Health v1.2 - Physical 2a		
Short Form Conversion Table		
Raw Summed Score	T-Score	SE*
2	23.4	5.5
3	29	5.1
4	33.4	4.9
5	37.3	4.8
6	41.1	4.8
7	45	5.1
8	50	5.4
9	56	5.9
10	63.3	7.1

*SE = Standard Error on T-score metric

From: http://www.healthmeasures.net/images/PROMIS/manuals/PROMIS_Global_Scoring_Manual.pdf

c. Physical Function measured by the PROMIS-Physical Function 4

This scale consists of four items, each scored from 1 to 5 with higher scores indicating better physical function. In the follow-up survey, these are the variables CHORES, STAIRS, WALK15M, and SHOP. These items will all have to be reverse-scored prior to summing. Missing items will not be imputed. A total score is computed by summing these four items, and is then converted to a t-score for analysis using the table below.³

² Updated 7/24/2022 – Rather than using the table values, we will have the PROMIS scales scored by the website https://www.assessmentcenter.net/ac_scoringservice, which will allow for some missing items. On this website, select “Existing short form or profile”, PROMIS, adult respondents, and global health domain, then search. Select “PROMIS scale v 1.2 – Global Health”, and select the default calibration sample.

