For each outcome measured using a scale, missing scale items will be imputed as described in Section 5 above. Data missing by design (e.g., due to a skip pattern in the data collection form) will be filled in logically where appropriate.

7. Analysis of Participant Follow-Up

We will present an account of the final disposition (completed, withdrew, lost, or died) for each participant in the ITT Population, including any admission violations and group assignment. The number and proportion of participants in the ITT population who provided information for the analyses of the study objectives will be summarized by randomization group. Frequencies of participants with missing primary outcome data will be summarized by randomization group and study visit. We will provide a CONSORT diagram showing the flow of participants through the trial, indicating withdrawals by treatment arm with reasons, when provided.

8. Analysis of Baseline Data

We will summarize baseline data (i.e., pre-randomization data) for the ITT Population, by randomization group, site type (ED vs. Urgent Care), and overall. Measures of central tendency and dispersion for continuous and certain discrete variables will include means, standard deviations, medians, minima, and maxima. Categorical data will be summarized with frequencies and percentages. Some continuous variables may also be grouped into categorical levels and evaluated in frequency tables. No inferential statistics (i.e., p-values and/or confidence intervals) for comparing data between groups will be presented.

9. Primary Analysis of Primary Outcome (Objective 1)

The primary analysis of BPI-SF will use the ITT Population, and will be repeated secondarily using the Per-Protocol Population. We will use a linear mixed model to conduct an analysis of covariance (ANCOVA), controlling for site type (ED vs. Urgent Care), baseline pain severity, age, gender, race,

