comorbidity score, baseline intermittent opioid use, a history of chronic pain, and access to a PCP (access to a PCP was used to stratify the randomization and, as such, it is important to control for it in all models). These control variables were selected a priori based on prior evidence of prognostic value and will not be subjected to significance testing. This model will include all pain severity scores (1, 3, 6, and 12 months) as outcomes; will include fixed effects for group, visit, and group-by-visit; and will use an unstructured covariance matrix for the error terms. We will first test a 6 degrees of freedom (df) linear contrast of the overall null hypothesis of no mean difference in the primary outcome at any of the 1-, 3-, and 6-month follow-up assessments across the 3 groups at the 5% significance level. If the overall null hypothesis is rejected, we will then conduct two separate 3 df contrasts to compare each of the intervention groups with the control group using a Bonferroni-adjusted 2.5% significance level. We will secondarily estimate mean pairwise differences along with 95% confidence intervals at each time point, including data collected at the 12-month follow-up time point.

10. Secondary and Exploratory Analyses (Objective 1)

The same linear mixed modeling approach used for the primary outcome will be applied to each of the separate components of the BPI-SF (Pain Severity and Interference). Similar comparisons using the sequence of linear contrasts and 95% confidence intervals as specified for the primary outcome will be made.

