Similar longitudinal modeling approaches will be applied to evaluate treatment effects on other secondary outcome variables. Appropriate models will be applied depending on the scale of the outcome variable, but the model for fixed effects/linear component will remain consistent across outcomes. For opioid use, a binary outcome, we will apply generalized estimating equations along with a logistic link function and unstructured working covariance matrix. For analgesic-related side effect frequency and severity, physical function, overall health, sleep quality, and healthcare utilization, all quantitative measures, we will compare mean response over time by applying generalized estimating equations along with an identity link function and unstructured working covariance matrix. All comparisons will be made using appropriately specified linear contrasts, tested at the 5% significance level, and/or 95% confidence intervals.

Non-opioid analgesic use and use of other pain management strategies will be descriptively summarized by randomization group and time, without any plans to apply inferential statistical methods (hypothesis tests or confidence intervals).

Exploratory Analyses: To assess whether some groups of participants are more likely to benefit from the interventions, we will estimate and compare effects using tests of interaction for a priori identified subgroups based on gender, race, health literacy, access to a PCP, and preference for control over decision-making⁴. To assess for potentially differential intervention effects on the primary outcome across each of the subgroups, we will use ANCOVA models similar to that for the primary analysis, but with the addition of appropriate interactions between intervention groups and subgroups. Separate models will be used to assess each interaction. Interpretation of differential effects of the intervention will be limited to subgroups for which an interaction is significant at the 5% level.

⁴ After enrollment was converted to remote due to COVID, which meant that the intervention was experienced following the ED visit, the shared decision making items were dropped from the study. Thus, we will not use “preference for control over decision-making” as a variable in our models.

11. Assessing Potential Mechanisms (Objective 2)

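### SAP Section 10, as written, omits physical function's and overall health's own baselines from their models, and the protocol conflicts on whether baseline pain interference, half of the primary score, was collected

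*Protocol*

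**What the plan says.** The SAP states that it "supersedes the summary plan included in the study protocol", so its models govern.

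- **Primary score.** SAP Section 5a defines the combined score as one "which will be obtained by averaging the Pain Severity and Pain Interference scores, assuming that neither is missing". Interference therefore carries half the weight. The protocol synopsis averages 11 items instead, which gives interference 7/11, or 64%.
- **Primary covariates.** SAP Section 9 specifies an ANCOVA "controlling for site type (ED vs. Urgent Care), baseline pain severity, age, gender, race", followed by "comorbidity score, baseline intermittent opioid use, a history of chronic pain, and access to a PCP". Severity is the only baseline BPI component; eight other covariates accompany it. Protocol 6.1 has the same structure.
- **Secondary models.** SAP Section 10 says that "the model for fixed effects/linear component will remain consistent across outcomes". It mentions no own-baseline term for any secondary outcome.
- **Baseline BPI.** The baseline list in Protocol 5.2 includes the instrument with this description: "The BPI-SF is an 11-item measure that rates pain severity and interference over the past week". The schedule in 5.4 marks "Brief Pain Inventory-short form (pain severity only" at baseline and has a separate severity-and-interference row marked only from week 1.
- **Baseline PROMIS.** Protocol 5.2 lists both PROMIS scales at baseline. The schedule marks each twice there: once referring to the time before the pain, and once including pain. The second form is the one used at follow-up.

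**The concern.** The baseline value of an outcome is usually among its strongest predictors. Leaving out one that has already been collected gives up precision for nothing. For physical function and overall health, that is what SAP Section 10 implies when read as written.

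For the primary outcome, a reader cannot tell from the protocol whether a baseline value of the combined score exists. If it does, the model uses only half of it. If it does not, the documents should say so. The comparison with most to gain is video-only against usual care, one of the two confirmatory contrasts, with a stated power of 67%.

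**Working it through.** **Inputs from Protocol 6.2.** 120 per group; 20% loss at 12 months; effects of 20% (full) and 15% (video-only); pairwise tests at 2.5%; power about 93% and 67%; up to 10% admitted; 400 enrolled. SAP Section 9 gives 3 df for each pairwise contrast.

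**Step 1. Reproduce the plan's figures.** 3 × 120 / 0.90 = 400, as stated. The power values cannot be rebuilt from scratch because the means and covariances are in figures that are not available. They can be checked against each other. With a noncentral chi-square (3 df, alpha 0.025, critical value 9.35), 93% power needs noncentrality 18.09. Scaling by (15/20)² gives 10.18, hence 67.7% for video-only (stated 67%). In the other direction, 67% needs 10.05; multiplied by (20/15)² this gives 92.7% (stated 93%). The two figures agree.

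**Step 2. Effect of one more prognostic covariate.** If the added baseline explains a share R² of the residual variance at every visit, the standard error is multiplied by √(1 − R²) and the noncentrality by 1/(1 − R²). R² is an assumption; the documents give no value. Noncentrality starts at 10.05 for 120 per arm, and at 10.05 × 133.3/120 = 11.17 for 400/3 = 133.3 per arm.

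| Assumed partial R² | SE multiplier | Video-only power, 120 per arm | Video-only power, 133.3 per arm | Size equivalent to 400 |
|---|---|---|---|---|
| 0 | 1.000 | 67.0% | 72.7% | 400 |
| 0.02 | 0.990 | 68.1% | 73.7% | 408 |
| 0.05 | 0.975 | 69.8% | 75.3% | 421 |
| 0.10 | 0.949 | 72.7% | 78.1% | 444 |

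The 133.3 column is a rescaling and does not appear in the protocol.

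**Step 3. How wide could R² be for baseline interference?** Let a be the correlation of baseline severity with baseline interference, and r_s and r_i the correlations of the outcome with each. Then R²_both = (r_s² + r_i² − 2·r_s·r_i·a)/(1 − a²), and partial R² = (R²_both − r_s²)/(1 − r_s²). All correlations here are assumptions.

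- a = 0.7, r_s = 0.4, r_i = 0.3: R²_both = 0.082/0.51 = 0.161; partial R² = 0.001.
- a = 0.7, r_s = 0.3, r_i = 0.5: R²_both = 0.130/0.51 = 0.255; partial R² = 0.18.

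Over a = 0.5-0.7, r_s = 0.3-0.4 and r_i = 0.3-0.5, partial R² runs from about 0.001 to 0.18, so the standard error falls by between 0% and about 10%. If interference was not asked at baseline, the gain from it is exactly zero.

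**Step 4. Which secondary outcomes are affected?** The Pain Severity component already has its own baseline in the model. The Interference component shares the primary outcome's uncertainty. For opioid use, baseline intermittent use is already a covariate. The schedule has no baseline entry for analgesic side effects or sleep, so nothing can be added there. Physical function and overall health have a scheduled baseline that is not in their models. No power is stated for them, so only the SE multiplier in the table carries over, again with R² assumed.

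**The case against.** The strongest reply is that baseline interference was probably never asked. The schedule's two separate BPI rows look deliberate, and every version of the model adjusts for severity alone. Protocol 5.2 may simply be giving the instrument's general description, which the follow-up lists reuse by cross-reference. This stands as the likelier reading. A reader might infer that the primary analysis discards available precision; the documents do not support that unless 5.2 describes what was done. Nor does the model adjust for severity alone, given the eight other covariates, among them chronic pain history and intermittent opioid use.

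A second reply is that consistency in SAP Section 10 may refer only to the group, visit and interaction terms, since the section speaks of similar approaches. That is possible. But no own-baseline term is named anywhere, so a programmer following the text would leave it out.

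Third, baseline PROMIS Physical Function is not a proven substitute for interference. It has four items on chores, stairs, walking and errands, against seven interference items. Its including-pain form at baseline rests on the schedule alone, and the schedule also marks PROMIS at week 1, where the questionnaire lists in 4.5 and 5.3 do not. This stands, and makes the scale an optional proxy only.

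Finally, the SAP has no rule for missing covariates, so an added questionnaire score could drop ITT participants and offset the gain. This also stands, and the fix must deal with it.

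**Conclusion.** The point holds as one about precision and clarity. Taken as written, SAP Section 10 leaves physical function and overall health unadjusted for their own baselines, however the BPI conflict resolves. For the primary outcome there is an unresolved contradiction between Protocol 5.2 and 5.4, and a gain from baseline interference only if it was collected.

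The documents do not give the size of the gain, and it may be negligible. With an assumed partial R² of 0.05-0.10, video-only power moves from 67% to about 70-73% at 120 per arm, or from about 73% to 75-78% at 133 per arm. These figures are illustrative: Protocol 6.2 computed power for pain severity, not the combined score, and Step 2 applies one R² to all visits.

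A reader might infer bias from unadjusted chance imbalance, or an error in the stated power. Neither follows. The randomised comparison is unbiased, chance imbalance is already reflected in the standard error, type I error is unaffected, and the stated powers agree with each other.

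**What to change.** Before unblinding, and recorded as a dated SAP change:

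1. In SAP Section 10, add each secondary outcome's own baseline value to its model where collected. For the two PROMIS scales, name the form that enters; the including-pain form matches follow-up.
2. Reconcile Protocol 5.2 with 5.4 and state in the SAP which BPI items were asked at baseline. If interference was collected, adjust the primary model and the Interference model for baseline interference, or for the combined score, as well as severity. If it was not, say so; baseline PROMIS Physical Function (including pain) is then an optional proxy.
3. Give a rule for missing baseline covariates, such as imputing the overall mean without using treatment arm, so that no ITT participant is lost from a model.

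The cost is a short amendment to the covariate list and one missing-data rule, with no new data. SAP Section 4 already provides for plan changes in blinded review. If unblinding has already taken place, the added terms belong in a labelled sensitivity analysis.
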